5.2.2 Assess the effect of Ampion compared to placebo on pulmonary function

- Change in blood oxygen saturation from baseline to Day 7; Day 28; Day 60

The hypotheses to be tested are:

$$H_0: \mu_A = \mu_S \text{ versus } H_A: \mu_A \neq \mu_S$$

Where μ_A and μ_S represent the percentage shift through day 7, 28, and 60 for Ampion and Placebo after randomization. The difference between Ampion and Placebo with respect to the percent change from baseline at day 7, 28, and 60 will be tested utilizing

a Wilcoxon rank-sum test via PROC NPAR1WAY. To assess any potential time trends an exploratory repeated measures analysis of variance will be performed with terms for treatment, time and the interaction between the two. This will be done utilizing PROC GLM with the REPEATED option.

- Change in six-minute walk test (6MWT) score from baseline to Day 7; Day 28; Day 60

The hypotheses to be tested are:

$$H_0: \mu_A = \mu_S \text{ versus } H_A: \mu_A \neq \mu_S$$

Where μ_A and μ_S represent the percentage shift through day 7, 28, and 60 for Ampion and Placebo after randomization. The difference between Ampion and Placebo with respect to the percent change from baseline at day 7, 28, and 60 will be tested utilizing a Wilcoxon rank-sum test via PROC NPAR1WAY. To assess any potential time trends an exploratory repeated measures analysis of variance will be performed with terms for treatment, time and the interaction between the two. This will be done utilizing PROC GLM with the REPEATED option.

5.2.3 Assess the effect of Ampion compared to placebo on global impression

- Change in Quality-of-Life Assessment using SF-36 from baseline to Day 7; Day 28; Day 60
- Change in Fatigue questionnaire from baseline to Day 7; Day 28; Day 60
- Change in Sleep Disturbance questionnaire from baseline to Day 7; Day 28; Day 60

The hypotheses to be tested for all three assessments are:

$$H_0: \mu_A = \mu_S \text{ versus } H_A: \mu_A \neq \mu_S$$

Where μ_A and μ_S represent the percentage shift through day 7, 28, and 60 for Ampion and Placebo after randomization. The difference between Ampion and Placebo with respect to the percent change from baseline at day 7, 28, and 60 will be tested utilizing a Wilcoxon rank-sum test via PROC NPAR1WAY. To assess any potential time trends an exploratory repeated measures analysis of variance will be performed with terms for treatment, time and the interaction between the two. This will be done utilizing PROC GLM with the REPEATED option.

5.2.4 Assess the effect of Ampion compared to placebo on radiographic findings

- Change in chest imaging on ground-glass opacity, local patchy shadowing, bilateral patchy shadowing, and/or interictal abnormalities from baseline to Day 60. These changes will be assessed qualitatively with descriptive information presented.

6 GENERAL CONSIDERATIONS

6.1 TIMING OF ANALYSES

An interim analysis for safety and efficacy endpoints will be performed once all subjects have completed their Day 28 assessments. The final analysis will be performed after all subjects have completed the study.

6.2 ANALYSIS POPULATIONS

6.2.1 Safety Analysis Population

The safety analysis population is defined as all patients who are randomized and receive any study medication. Participants will be analyzed as treated.

6.2.2 Intent-to-treat Population

The intent-to-treat (ITT) analysis population is defined as all randomized patients. All efficacy analyses will be performed in the ITT population. Patients will be analyzed as randomized.

6.3 MISSING DATA

All data collected under this study protocol will be included in the assessment of patient safety. Missing or incomplete AE data will assume greatest relationship to study drug and/or severity.

6.4 INTERIM ANALYSES AND DATA MONITORING

The interim analysis will involve unblinded data. Only a small, sequestered team will have access to the unblinded data and results. The data will not be transferred, or results viewed by any person involved in the day-to-day conduct of the clinical trial, including, but not limited to the blinded sponsor staff, Medical Monitor, and/or blinded CRO staff. These individuals will remain blinded to the results.

The unblinded team will be responsible for obtaining the required material for the analysis from the study's unblinded data manager (DM) for the clinical trial. The unblinded team will present the results of the interim analysis to the sponsor in a blinded fashion.

All individuals on the sequestered team who are unblinded will be documented and archived by the sponsor

A Data Safety Monitoring Board (DSMB) will be established to review the safety, as the study progresses, of IV Ampion. The DSMB will be primarily responsible for reviewing any serious Adverse Event (SAE) and other clinically important safety findings (e.g., discontinuations due to AEs) that may occur during the study. The study may be stopped upon recommendation by the DSMB.

7 SUMMARY OF STUDY DATA

Data will be summarized by each treatment arm and by pooled Control and Ampion arms. Descriptive statistics on continuous variables will include mean, standard deviation, median, 25th, and 75th percentiles, and range. Change from baseline will include a 95% confidence interval. Categorical variables will be summarized using frequency counts and percentages. Data listings of individual subject's data will be provided.

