Unless otherwise specified, continuous variables will be summarized with the number of non-missing observations, mean, standard deviation, median, minimum, maximum, and 95% confidence intervals displayed. Categorical data will be summarized as counts, percentages, and 95% confidence intervals.

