3.2 RANDOMIZATION AND BLINDING

The treatment in this study will be blinded to the subjects, investigators, any individual conducting the study (e.g., nursing and pharmacy staff) and clinical study personnel. Participants will be assigned to treatment by a randomization schedule developed and maintained by an independent statistician.

Participants are randomized 1:1 to active treatment or placebo control, following an equal allocation to treatment arms as follows:

Treatment Arm	Investigational Treatment
Active	Ampion Inhalation for 5-days
Control	Placebo Inhalation for 5-days

Given the changing nature of the pandemic, periodic adjustments to the allocation ratio may be made in an effort to achieve equal allocation across the treatment arms at the end of the enrollment.

Study drug and placebo will be provided as blinded investigational product (IP) with appropriate labeling to link to the randomization code. Where required, safety personnel and/or investigator may be unblinded to a particular subject's treatment assignment to meet reporting requirements to Regulators.

A data management plan and statistical analysis plan will be approved by the sponsor prior to unblinding study data.

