4 SAMPLE SIZE

This is a Phase I study and is not intended to be powered for the primary endpoint. This trial is designed to enroll up to 30 subjects, randomized to active treatment or placebo control, following an equal allocation to treatment arms (n=15 subjects per arm).

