5 STUDY ENDPOINTS AND ANALYSES

5.1 PRIMARY ENDPOINT

The primary endpoint is incidence and severity of adverse events (AEs) and serious adverse events (SAEs) from baseline to Day 28.

The hypotheses to be tested are:

$$H_0: \pi_A = \pi_S \text{ versus } H_A: \pi_A \neq \pi_S$$

Where π_A and π_S represent the adverse event rates for Ampion and placebo during the first 28 days after randomization.

The difference between Ampion and Placebo will be tested using the appropriate chi-square test or Fisher's exact test utilizing PROC FREQ with the EXACT option, if necessary.

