8.2 ADVERSE EVENTS

Adverse events (AEs) will be evaluated from baseline through Day 60. The primary endpoint is incidence and severity of adverse events (AEs) and serious adverse events (SAEs) from baseline to Day 28. The primary endpoint analysis is presented in Section 5.1.

There will be no statistical tests for incidence and severity of AEs. AEs will be tabulated using descriptive statistics and shift tables of lab tests will be presented for safety assessment.

All reported AEs, will be listed, documenting the course, outcome, severity, and causality to study drug. Verbatim terms on CRFs will be mapped to preferred terms and related system organ class using the Medical Dictionary for Regulatory Activities (MedDRA).

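### The SAP plans no confidence interval for the primary AE/SAE incidence, so with about 15 participants per arm the main result would carry no stated precision

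*SAP*

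**What the plan says.** **Endpoint and size.** SAP 5.1: "The primary endpoint is incidence and severity of adverse events (AEs) and serious adverse events (SAEs) from baseline to Day 28". SAP 3.2: "Participants are randomized 1:1 to active treatment or placebo control". SAP 4 sets an upper limit of 30 participants, "following an equal allocation to treatment arms (n=15 subjects per arm"), and adds: "This is a Phase I study and is not intended to be powered for the primary endpoint".

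**Summary rule in the SAP.** SAP 7 grants one interval: "Change from baseline will include a 95% confidence interval". The next sentence reads: "Categorical variables will be summarized using frequency counts and percentages".

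**Safety section.** SAP 8.2: "AEs will be tabulated using descriptive statistics and shift tables of lab tests will be presented for safety assessment". It says AE incidence and severity will not be tested, yet refers the reader to SAP 5.1 for the primary analysis. SAP 5.1 sets up a two-sided comparison of AE rates by chi-square or Fisher's exact test. Protocol 9.4.1 also rules out tests. The titles of Tables 10.3.2 and 10.3.3 in SAP 12.1 mention no interval.

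**Summary rule in the protocol.** Protocol 9.3: "Categorical data will be summarized as counts, percentages, and 95% confidence intervals". That sentence stands after the 9.3.1.5 Efficacy Data heading, in a paragraph that opens by allowing for exceptions. The protocol's safety text (9.3.1.4 and 9.4.1) names no interval. Protocol 9.4.2 names 95% intervals for the exploratory efficacy endpoints.

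**The concern.** The trial is unpowered by design, so its useful output on safety is an estimate together with its uncertainty. As the SAP stands, the exploratory change-from-baseline results get an interval and the primary endpoint does not, either within an arm or for Ampion minus placebo.

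At this sample size the precision matters more than the percentage. A table entry of 0 (0.0%), or equal counts in the two arms, does not show how much excess harm the data leave open. If SAP 5.1 is followed, a p-value stands beside the percentages, and a large p-value from 15 v 15 is easily taken as absence of a difference. The protocol says the data will inform further clinical development, so the rate of harm not excluded is what a later reader needs.

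**Working it through.** The documents give no power, precision or event-rate figure, so there is none to reproduce. Two arms of 15 give the stated 30.

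**Inputs.** n = 15 per arm (SAP 4). Two-sided 95% confidence is an assumption, since no interval method is named for AE rates. Event counts and true rates below are illustrative. z² = 1.96² ≈ 3.84.

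**1. One arm, no events.** The exact (Clopper-Pearson) two-sided 95% upper limit is 1 − 0.025^(1/n).
- n = 15: 1 − 0.025^(1/15) = 21.8%.
- Other conventions at n = 15: one-sided exact, 1 − 0.05^(1/15) = 18.1%; rule of three, 3/15 = 20.0%; Wilson, z²/(n + z²) = 3.84/18.84 = 20.4%.
- With fewer treated participants the exact two-sided limit rises: 23.2% at n = 14, 24.7% at n = 13, 26.5% at n = 12.

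**2. One arm, a few events (exact two-sided 95%).**

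| Events | Percentage | 95% interval |
|---|---|---|
| 1/15 | 6.7% | 0.2% to 31.9% |
| 2/15 | 13.3% | 1.7% to 40.5% |
| 3/15 | 20.0% | 4.3% to 48.1% |
| 5/15 | 33.3% | 11.8% to 61.6% |

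**3. Chance of a zero count.** P(0 of 15) = (1 − p)^15. At p = 5%, 0.95^15 = 46.3%. At p = 10%, 0.90^15 = 20.6%.

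**4. Difference between arms.** With Wilson limits l and u for each arm, Newcombe's upper limit is d + √[(u₁ − p₁)² + (p₂ − l₂)²]. The lower limit is d − √[(p₁ − l₁)² + (u₂ − p₂)²].
- 0/15 v 0/15: l = 0, u = 0.204, so the interval is 0 ± √(0.204² + 0²) = ±20.4 points.
- 5/15 v 5/15: l = 0.152, u = 0.583, so the interval is 0 ± √(0.250² + 0.182²) = ±30.9 points.

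**5. Does the SAP 5.1 test fill the gap?** Fisher's exact test at 15 v 15:

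| Split | p |
|---|---|
| 0 v 0 | 1.00 |
| 0 v 2 | 0.48 |
| 0 v 3 | 0.22 |
| 0 v 4 | 0.0996 |
| 0 v 5 | 0.042 |

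Against an arm with no events, five events are needed before p falls below 0.05. If the true rates were 21.8% and 0%, the test would reject at the two-sided 5% level with probability 21%. The p-value gives no range for the difference.

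**The case against.** Four objections carry weight.

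**The protocol may never have promised these intervals.** A reader might infer that the SAP removes something the protocol requires. The documents do not establish that. The protocol sentence follows the efficacy heading, and the protocol's own safety text names no interval. The opposite reading is possible, because the sentence is worded generally and closes the data-presentation section. The gap does not depend on which is right. Either the SAP omits a protocol provision without recording the change, or neither document gives the primary endpoint an interval.

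**The SAP plans more than counts and percentages.** That is true: SAP 5.1 plans a test. But a test does not measure precision, and this one conflicts with SAP 8.2 and Protocol 9.4.1.

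**Nobody has said that zero events means safe.** A reader might infer that the plan would treat a zero count as proof of safety. No passage sets such a rule, and both documents state that the study is not powered. Misreading is a risk, not a plan. Protocol 2.3 makes it plausible, since it describes a 10-subject intravenous study as having found the product safe, without an interval. The evidence there is mixed: its overall safety statement on the 27-subject inhalation study is hedged.

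**Intervals can be computed later from the counts, and table titles would not normally announce them.** Both are fair. No estimate or population is made wrong by the omission, and titles alone are weak evidence. But SAP 7 states the rule for categorical data directly, and an interval chosen after unblinding leaves the method open.

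**Conclusion.** The concern holds as a reporting gap in the primary result. It is not a sample-size error or a flaw that invalidates the design. The SAP names no interval for AE or SAE incidence in 5.1, 7, 8, 8.2 or the table list. At 15 per arm, a zero count leaves rates up to 21.8% unexcluded (exact, two-sided 95%; 18% to 20% under the other conventions shown), and equal counts leave differences of about ±20 to ±31 points open.

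These figures assume 15 treated participants in each arm and 95% confidence. The 21.8% is not a fixed property of the trial: SAP 6.2.1 counts only participants who received study medication, enrolment is capped at 30 and not guaranteed, and the limit moves with n and method.

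**What to change.** 1. In SAP 5.1, 7, 8.2 and Tables 10.3.2 and 10.3.3, report the number and percentage of participants with any AE, any severe AE and any SAE over the primary window.
2. Settle that window. SAP 5.1, SAP 8.2 and Protocol 9.4.1 say Day 28, while SAP 2.3.1 and Protocol 3.3.1 say Day 28 and Day 60.
3. Give an exact (Clopper-Pearson) two-sided 95% interval per arm and a named non-Wald 95% interval, such as Newcombe, for Ampion minus placebo. A Wald interval has zero width at 0/15. Footnote both methods, because they are built differently: at 0 v 0 the Newcombe limit for the difference (20.4 points) is smaller than the exact single-arm limit (21.8%).
4. Make these estimates the primary presentation in place of the SAP 5.1 test, or reconcile SAP 5.1 with SAP 8.2 and Protocol 9.4.1.
5. Where an arm has no events, state the rate not excluded, computed from the observed number treated and with the method named.

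**Cost.** A SAP amendment before unblinding and a few lines of code, with no extra participants or visits. The safety statement will read less favourably.

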7.1 SUBJECT DISPOSITION

The number of subjects who are randomized, receive study drug, and complete the study will be summarized. The number of subjects included in the safety and ITT analysis sets will be included in the table. Attendance at each assessment (see Schedule of Assessments), including missed visits, discontinuations, lost to follow-up, and percentage accountability will be summarized. A list of subjects who withdraw early will be provided. It will include the reason and timing of the withdrawal. Similarly, the reason any subject is excluded from an analysis set will also be provided.

7.2 PROTOCOL DEVIATIONS

Significant known protocol deviations will be noted for individual subjects; a summary table may also be provided.

7.3 DEMOGRAPHIC AND BASELINE VARIABLES

Age, gender, race, height and weight, and comorbidities will be summarized by treatment arm for all subjects receiving study drug, using descriptive statistics.

Comparability of demographic and baseline characteristics will be evaluated between the Placebo and Ampion arms. Comparisons will use a two-sample t-test/Wilcoxon rank-sum test for continuous variables or a chi-square test (or Fisher's exact test if any expected value is less than 5) for categorical variables.

The following demographic and baseline characteristics will be evaluated:

- 1) Age (calculated as [date of study entry-date of birth]/365.25)
- 2) Gender
- 3) Race
- 4) Height
- 5) Weight

7.4 MEDICAL HISTORY AND PHYSICAL EXAM

The number and percent of participants with past and current medical disorders at the time of randomization will be presented overall and by treatment group for the ITT analysis population.

The following variables will be included:

- 1) Medical history term

8 SAFETY EVALUATION

The safety analyses of exposure, AEs, concomitant medications, and vital signs will include descriptive statistics and will be summarized separately by treatment arm and overall.

Summaries of AEs will be generated by type (AE or SAE), body system and preferred term, severity, and relationship to study product.

8.1 EXPOSURE

Total exposure to the test product or placebo will be calculated by treatment arm. Descriptive statistics will be presented.

8.2 ADVERSE EVENTS

Adverse events (AEs) will be evaluated from baseline through Day 60. The primary endpoint is incidence and severity of adverse events (AEs) and serious adverse events (SAEs) from baseline to Day 28. The primary endpoint analysis is presented in Section 5.1.

There will be no statistical tests for incidence and severity of AEs. AEs will be tabulated using descriptive statistics and shift tables of lab tests will be presented for safety assessment.

All reported AEs, will be listed, documenting the course, outcome, severity, and causality to study drug. Verbatim terms on CRFs will be mapped to preferred terms and related system organ class using the Medical Dictionary for Regulatory Activities (MedDRA).

8.3 CONCOMITANT MEDICATIONS

The number and percent of subjects receiving concomitant medications or therapies prior to and during the study and at the final visit will be tabulated and presented overall and by treatment group for the ITT analysis population.

Concomitant medications/treatments will be summarized using descriptive statistics and will be presented by type of drug (WHO DRUG classification) overall and by treatment group for the safety and ITT analysis populations. There should be no significant differences in the use of concomitant treatments between groups. Differences will be assessed using a chi-square or Fisher's exact test.

8.4 VITAL SIGNS

Vital signs will be listed for each subject. These will include temperature, respiration, pulse, and blood pressure. Summaries over time and changes from baseline will be provided.

9 TECHNICAL DETAILS

All analyses will be conducted using SAS Version 9.4. MedDRA Version 24.0 will be used to code adverse events and medical history conditions.

10 CHANGES IN CONDUCT OF STUDY OR TO PLANNED ANALYSES FROM PROTOCOL

Deviations from the statistical analyses outlined in this plan will be indicated; any further modifications would be noted in the final statistical analyses.

11 REFERENCES

12 LISTING OF TABLES, LISTINGS, AND FIGURES

12.1 TABLES

10.1 Accountability

10.1.1	Accountability (Analysis population: All Enrolled)
10.1.2	Analysis Populations (Analysis population: All Enrolled)
10.1.3	Subject Disposition (All Screened)
10.1.4	Major Protocol Deviations (Analysis population: All Enrolled)
10.1.5	Demographics and Baseline Characteristics (Analysis population: ITT)

10.2 Efficacy (Analysis population: ITT)

10.2.1	Summary of Change in FDA Assessment of 14 Common COVID-19-Related Symptoms
10.2.2	Summary of Change in Borg Dyspnoea Scale
10.2.3	Summary of Change in All-Cause Mortality
10.2.4	Summary of Change in Blood Oxygen Saturation
10.2.5	Summary of Change in Six-Minute Walk Test
10.2.6	Summary of Change in SF-36 Quality of Life Assessment
10.2.7	Summary of Change in Fatigue Questionnaire
10.2.8	Summary of Change in Sleep Disturbance Questionnaire
10.2.9	Summary of Change in Chest Imaging

10.3 Safety

10.3.1	Exposure to Study Treatment
10.3.2	Incidence and Severity of Treatment-Emergent (TEAE) Events from Baseline to Day 28
10.3.3	Incidence and Severity of Serious Treatment-Emergent (TEAE) Events from Baseline to Day 28
10.3.4	Overall Summary of Treatment-Emergent Adverse (TEAE) Events
10.3.5	Incidence of TEAEs by System Organ Class and Preferred Term
10.3.6	Incidence of Treatment-Emergent Related AEs by System Organ Class and Preferred Term
10.3.7	Incidence of Treatment-Emergent Serious Adverse Events (SAEs) by System Organ Class and Preferred Term
10.3.8	Incidence of TEAEs by Preferred Term in Descending Order of Frequency

10.3.9	Incidence of Treatment-Emergent Related AEs by Preferred Term in Descending Order of Frequency
10.3.10.1	Summary of Pulse Change from Baseline over Time (bpm)
10.3.10.2	Summary of Body Temperature and Change from Baseline over Time (F)
10.3.10.3	Summary of Systolic BP and Change from Baseline over Time (mmHg)
10.3.10.4	Summary of Diastolic BP and Change from Baseline over Time (mmHg)
10.3.10.5	Summary of Respiration Rate and Change from Baseline over Time
10.3.11.1	Concomitant Medication Use by ATC Level 1
10.3.11.2	Concomitant Medications Preferred Term in Descending Order of Use
10.3.11.3	Medication Started on Study Preferred Term in Descending Order of Use

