Reference Therapy, Dose and Mode of Administration: Participants in the control arm will inhale nebulized placebo (8 mL) administered four times daily for 5 days. Nebulized placebo will be delivered using the Aerogen Solo Nebulizer System with the Aerogen Solo Adaptor (FDA 510K K133360) manufactured by Aerogen Limited, Galway, Ireland. The Aerogen Solo Adaptor is a vibrating mesh nebulizer with a drug reservoir used for delivery of respiratory therapy, including the hand-held Aerogen Ultra. Medications will be recorded as concomitant medication, tabulated, and compared among groups.	
Study Duration: Treatment: 5 days Follow-up: 60 days	

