6 DISCONTINUATION CRITERIA

6.1 Early Discontinuation of the Study

Discontinuation or temporary suspension is allowed for any reason. The Sponsor may suspend or terminate the study due to the development of any new or unexpected life threatening or adverse events, prolonged hospitalization, or other potential grounds for stopping the study. The number of subjects, as well as the types and the grade severity of the adverse events (according to Common Terminology Criteria for Adverse Events (CTCAE)) may trigger the temporary suspension of study product administration pending a safety investigation as follows:

If any nebulization reactions of grade 3 and above (as defined using the CTCAE grading scale version 5.0 or newer) are observed in any patient within 24 hours of product administration, a safety investigation will occur, which may trigger the temporary suspension of study product administration.

It is agreed that for reasonable cause, either the investigator or the Sponsor may terminate this study, provided written notice is submitted at a reasonable time in advance of intended termination; if by the investigator notice is to be submitted to Ampio Pharmaceuticals, Inc., and if by the Sponsor, notice will be provided to each investigator.

If a severe local reaction or drug-related SAE occurs at any time during the study, the DSMB will review the case immediately.

The study will be immediately suspended and no additional Ampion treatments administered pending review and discussion of all appropriate study data by the DSMB if one or more participants develop any of the following adverse events deemed to be possibly, probably, or definitely related to Ampion by the Investigator and/or Medical Monitor, based upon close temporal relationship or other factors:

- Death
- Respiratory deterioration requiring extracorporeal membrane oxygenation (ECMO)
- Anaphylaxis
- Acute adverse reaction at administration of treatment (i.e., sudden change in vital signs)

The study will not be restarted until all parties have agreed to the course of action to be taken and the IRB/EC has been notified.

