7.1 Dosing and Administration of Study Medication

Study treatment (Ampion or placebo) will be provided as a solution in vials ready for human use and treatment administration. The participant will be trained to self-administer the study treatment. Treatment should start within 24 hours of randomization and should terminate on last treatment day (Day 5).

Study treatment (Ampion or placebo) will be delivered by inhalation using a nebulizer as a 32mL daily dose administered four times daily (8mL per treatment) every four to six hours for five days.

Study treatment (Ampion or placebo) is presented as a sterile liquid in a glass vial. For each use, the contents of are transferred to the drug reservoir in the nebulizer and nebulized continuously until the drug is fully administered.

Study treatment (Ampion or placebo) is aerosolized for inhalation using the Aerogen Ultra handheld nebulizer (Aerogen Limited, Galway, Ireland, FDA 510K K133360), which consists of the Aerogen Pro-X Controller and the Aerogen Ultra handheld unit. The system is a portable medical device for single patient use indicated for aerosolization of physician-prescribed solutions for inhalation. Ampion is nebulized using the continuous setting on the Aerogen controller, and the study drug is nebulized until it is fully aerosolized.

Product administration may be temporarily suspended until resolution if a serious, or sudden side effects are observed. The nature of the event will be evaluated (i.e., allergic; localized; systemic or otherwise) and appropriate measures applied, which may include symptomatic treatment with antihistamines and antiallergic measures, paracetamol (acetaminophen) and/or corticosteroids.

As described in [Section 6.1](#), if any reactions of grade 3 and above (as defined using the CTCAE grading scale version 5.0 or newer) are observed in any patient within 24 hours of product administration, a safety investigation will occur, which may trigger the temporary suspension of study product administration.

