9.3 Data presentation

9.3.1.1 Demographic and Baseline Characteristics:

Demographic (e.g., age, sex, race, ethnicity) and baseline characteristics (e.g., weight, height, comorbidities) summarized using descriptive statistics, overall and by treatment group for the ITT analysis population.

9.3.1.2 Medical History and Physical Examination:

The number and percent of participants with past and current medical disorders at the time of randomization will be presented overall and by treatment group for the ITT analysis population.

9.3.1.3 Concomitant Medications or Treatments:

The number and percent of subjects receiving concomitant medications or therapies prior to and during the study and at the final visit will be tabulated and presented overall and by treatment group for the ITT analysis population.

Concomitant medications/treatments will be summarized using descriptive statistics and will be presented by type of drug (WHO DRUG classification) overall and by treatment group for the

safety and ITT analysis populations. There should be no significant differences in the use of concomitant treatments between groups. All concomitant therapies will be recorded to be able to compare any inadvertent imbalances between the groups.

9.3.1.4 Safety Data:

Safety data will be presented by treatment arm. Safety data will be evaluated by changes in the frequency and severity of AEs. Concomitant medication will be recorded for safety. AEs will be collected from baseline to Day 60. The severity of AEs (mild, moderate, severe), relatedness (related, possibly related, unrelated) along with the duration, action taken, and outcome (e.g., study withdrawal) will also be recorded.

All data collected under this study protocol will be included in the assessment of patient safety. Missing or incomplete AE data will assume greatest relationship to study drug and/or severity.

Remaining safety data will be collected from enrollment until study exit (or death). Safety data will be tabulated and presented overall and by treatment group for the safety analysis population.

9.3.1.5 Efficacy Data:

The efficacy of treatment on the clinical course and outcome of COVID-19 will be evaluated by treatment arm. Summaries will be performed by treatment arm (active or control).

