2.3 ENDPOINTS

2.3.1 Primary

Adverse events (AEs) will be evaluated from baseline through Day 60. The primary endpoint is incidence and severity of adverse events (AEs) and serious adverse events (SAEs) from baseline to Day 28 and Day 60.

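### No planned AE table is limited to, or split at, the end of the 5-day dosing period, so an excess confined to dosing is diluted in the Day 28 comparison

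*SAP*

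**What the plan says.** The Protocol synopsis gives "Study Duration: Treatment: 5 days Follow-up: 60 days". Protocol 7.1 ends treatment on Day 5.

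SAP 5.1 states: "The primary endpoint is incidence and severity of adverse events (AEs) and serious adverse events (SAEs) from baseline to Day 28". The quantities it compares "represent the adverse event rates for Ampion and placebo during the first 28 days after randomization". In the table list of SAP 12.1, Table 10.3.2 is "Incidence and Severity of Treatment-Emergent (TEAE) Events from Baseline to Day 28" and Table 10.3.3 is its counterpart for serious events. Tables 10.3.4 to 10.3.9 name no period, and the available text does not define treatment-emergent.

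Protocol 9.3 says "AEs will be collected from baseline to Day 60", and the schedule of assessments records AEs on each dosing day. Protocol 6.1 also uses a period "within 24 hours of product administration", but only to trigger a safety investigation of grade 3 or higher reactions.

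No table separates events that begin during dosing from later ones.

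**The concern.** The primary objective is the safety and tolerability of a 5-day inhaled course, in what SAP 2.1 calls the first at-home use in long-COVID. The risks named in Protocol 2.5 and 6.1 are largely acute: allergic reaction, flushing, nebulization reaction and anaphylaxis.

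Participants enter with at least two respiratory symptoms scored two or higher (Protocol 4.4), and any unfavorable symptom can qualify as an AE (Protocol 8.1). Background events in both arms are therefore plausible. If a participant counts once for any AE up to Day 28, someone who reacts to inhalation adds nothing to the difference between arms if a later unrelated event would have counted them anyway. What is at stake is how clearly the safety output can show an early excess, with only 15 per arm.

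**Working it through.** **Inputs from the documents.** Last dosing day: Day 5 (Protocol 7.1). Primary window: 28 days (SAP 5.1). Sample size: 15 per arm (SAP 4). Days of the primary window after the last dosing day: 28 − 5 = 23, and 23/28 = 82%.

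**No figure to reproduce.** The plan states no AE rate, effect size, power or numerical alpha, so 15 per arm cannot be re-derived.

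**Assumptions.** The background hazard is constant and equal in both arms, set by a 28-day background risk b of 10%, 20%, 40% or 60%. The drug independently causes an AE in d = 20% of active participants, all during dosing. The short window runs from first dose to 24 hours after last dose, taken as t = 6 days.

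**Formulas.**
- Hazard: λ = −ln(1 − b)/28
- Placebo risk to day t: p0 = 1 − exp(−λt)
- Active risk to day t: p1 = 1 − (1 − d)(1 − p0)
- Difference: p1 − p0 = d(1 − p0)
- SE = √{[p0(1 − p0) + p1(1 − p1)]/15}

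**Example, b = 40%.** λ = 0.5108/28 = 0.01824.
- Six days: p0 = 10.4%, p1 = 28.3%, difference 17.9 points, SE 14.0 points, ratio 1.28.
- Twenty-eight days: p0 = 40%, p1 = 52%, difference 12.0 points, SE 18.1 points, ratio 0.66.
- Gain: 1.28/0.66 = 1.9.

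| b | p0, 6 d | Difference, 6 d (points) | Diff/SE, 6 d | Difference, 28 d (points) | Diff/SE, 28 d | Gain |
|---|---|---|---|---|---|---|
| 10% | 2.2% | 19.6 | 1.73 | 18.0 | 1.29 | 1.3 |
| 20% | 4.7% | 19.1 | 1.55 | 16.0 | 0.99 | 1.6 |
| 40% | 10.4% | 17.9 | 1.28 | 12.0 | 0.66 | 1.9 |
| 60% | 17.8% | 16.4 | 1.04 | 8.0 | 0.46 | 2.3 |

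The Day 28 difference keeps exp(−22λ) of the six-day difference: 92%, 84%, 67% and 49% down the rows.

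**Power check.** This uses Fisher's exact test at an assumed two-sided alpha of 0.05, 15 per arm, with the short window cut at Day 5. For d = 20% and b from 10% to 70%, power is 8% to 16% at Day 5 and 3% to 12% at Day 28. For d = 40%, it is 70% against 45% at b = 10%, and 41% against 10% at b = 50%.

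**What the existing outputs add.** Tables 10.3.6 and 10.3.9 tabulate related AEs, but they rest on investigator causality. The SAP does not say whether possibly related events count, and SAP 6.3 sets missing relatedness to the greatest relationship, which can move background events into these tables. Listing 19 shows every AE by participant but makes no comparison by arm.

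**The case against.** The strongest reply is that this asks for an extra table and does not identify an error. Much of that stands.

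- A 28-day risk difference is a valid estimate of 28-day risk, and it captures delayed events that a dosing window would miss. A reader might infer that the comparison is biased toward no difference. It is not: it is diluted for early harm and answers a different question.
- A reader might infer that every AE summary runs to Day 28 or study end. The documents say so only for Tables 10.3.2 and 10.3.3. For 10.3.4 to 10.3.9 it is an inference from AE evaluation through Day 60.
- A reader might treat the 24-hour rule in Protocol 6.1 as the protocol's own analysis window. It triggers an investigation, so its absence from the tables is not an inconsistency.
- Serious acute reactions would not go unnoticed. Protocol 6.1 provides for investigation, suspension and review by the data safety monitoring board, independently of the Day 28 table. With 30 participants, listings can also be read case by case.
- The rates are assumed. Protocol 2.3 reports no AE difference for inhaled Ampion in AP-014, so the documents do not support a 20% excess. At low background the gain is modest.
- The trial is declared unpowered. With d = 20%, no ratio in the table reaches 1.96 in either window. SAP 8.2 and Protocol 9.4.1 also say AEs will not be tested, which conflicts with SAP 5.1.

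What survives is narrower. Neither investigator causality nor manual review provides a by-arm contrast for the dosing period, and dilution affects descriptive incidences whether or not a test is run.

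**Conclusion.** The point holds as a gap in the planned output. The plan has no by-arm AE summary for the dosing period, although its primary objective concerns a 5-day course and AEs are collected on each dosing day. Under constant background hazard and a 20% drug-caused risk confined to dosing, the shorter window raises difference/SE about 1.3-fold at 10% background and 1.6- to 2.3-fold at 20% to 60%. These figures illustrate the mechanism and do not predict this trial, because the documents supply no AE rates. The shorter window does not make the trial adequately powered, and Day 28 is a legitimate primary window. The gain is in interpretability, at low cost.

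**What to change.** Keep Day 28 as the primary window and make three changes to the SAP:

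1. Add to SAP 12.1 one descriptive table, by arm, of AE incidence, severity and relatedness by non-overlapping onset period: first dose to 24 hours after last dose; from then to Day 28; and Day 29 to Day 60. The second period should begin where the first ends. A column starting on Day 6 would overlap the 24-hour extension.
2. State the period covered by each of Tables 10.3.4 to 10.3.9, and define treatment-emergent.
3. Flag events whose onset was imputed to the first-dose date. SAP 13.1 does this for some partial or missing start dates, so a later event could otherwise inflate the dosing-period column.

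While these sections are open, reconcile the primary window (SAP 2.3.1 and Protocol 3.3.1 say "from baseline to Day 28 and Day 60", while SAP 5.1 stops at Day 28) and the conflict between SAP 5.1 and SAP 8.2 over testing AEs. The new table needs neither settled first.

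The cost is one extra table from onset dates already collected, and a slightly longer safety output.
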